The 1st 2 patients will be enrolled in dose level 1. The next cohort of 2 patients will not begin treatment until all patients in the current cohort have reached day 21. Each new cohort of 2 patients will be assigned by the study statistician to the most appropriate dose level based on toxicity probabilities set for this study. The MTD for each arm (high-risk and steroid-refractory aGVHD) will be identified when the total sample size of 20 patients within an arm is reached. Enrollment on phase I is expected to take 2 years based on an enrollment of approximately 20 patients per year for each arm.

Phase II Extension: After completion of the dose finding trial for each arm, the final doses will be carried forward into a two-stage phase II extension trial to confirm safety and make a preliminary determination of the activity level for Arm 1 and Arm 2. If the phase I trial enrolls fewer than 13 patients at the MTD, we will employ Simon's Minmax two-stage design with the possibility to discontinue after the 1st stage if the response rate is low.

- Stage 1: Enroll a total of 12 patients (including all treated at the MTD in phase I). *If 5 or more of these respond, the trial will continue to stage 2.*
- Stage 2: Enroll an additional 14 patients. *If 14 or more out of 26 patients respond, hCG will be considered promising for further investigation.*

If phase I trial enrolls more than 12 patients at the MTD, we will adjust the futility rule above for the two stage design with the giving number of patients enrolled at the MTD.

Arm 2A (steroid-dependent), Phase I: For each arm up to 5 dose levels of Pregnyl® will be tested; however dose levels -1 and -2 will be used only if dose level 1 proves too toxic. In addition to Pregnyl®, patients will continue on their current standard of care aGVHD treatment.

The 1st 2 patients will be enrolled in dose level 1. The next cohort of 2 patients will not begin treatment until all patients in the current cohort have reached day 21. Each new cohort of 2 patients will be assigned by the study statistician to the most appropriate dose level based on toxicity probabilities set for this study. The MTD for each arm (high-risk and steroid-refractory aGVHD) will be identified when the total sample size of 20 patients within an arm is reached. Enrollment on phase I is expected to take 2 years based on an enrollment of approximately 20 patients per year for each arm.

Phase II Extension: After completion of the dose finding trial for each arm, the final doses will be carried forward into a two-stage phase II extension trial to confirm safety and make a preliminary determination of the activity level for Arm 1 and Arm 2. If the phase I trial enrolls fewer than 13 patients at the MTD, we will employ Simon's Minmax two-stage design with the possibility to discontinue after the 1st stage if the response rate is low.

- **Stage 1:** Enroll a total of 12 patients (including all treated at the MTD in phase I). *If 5 or more of these respond, the trial will continue to stage 2.*
- **Stage 2:** Enroll an additional 14 patients. *If 14 or more out of 26 patients respond, hCG will be considered promising for further investigation.*

If phase I trial enrolls more than 12 patients at the MTD, we will adjust the futility rule above for the two stage design with the giving number of patients enrolled at the MTD.

Arm 2B (steroid-refractory), Phase I: For each arm up to 7 dose levels of Pregnyl® will be tested; however dose levels -1 and -2 will be used only if dose level 1 proves too toxic. In addition to Pregnyl®, patients will continue on their current standard of care aGVHD treatment.

The 1st 2 patients will be enrolled in dose level 1. The next cohort of 2 patients will not begin treatment until all patients in the current cohort have reached day 21. Each new cohort of 2 patients will be assigned by the study statistician to the most appropriate dose level based on toxicity probabilities set for this study. The MTD for each arm (high-risk and steroid-refractory aGVHD) will be identified when the total sample size of 20 patients within an arm is reached. Enrollment on phase I is expected to take 2 years based on an enrollment of approximately 20 patients per year for each arm.

Phase II Extension: After completion of the dose finding trial for each arm, the final doses will be carried forward into a two-stage phase II extension trial to confirm safety and make a preliminary determination of the activity level for Arm 1 and Arm 2. If the phase I trial enrolls fewer than 13 patients at the MTD, we will employ Simon's Minmax two-stage design with the possibility to discontinue after the 1st stage if the response rate is low.

- **Stage 1:** Enroll a total of 12 patients (including all treated at the MTD in phase I). *If 5 or more of these respond, the trial will continue to stage 2.*
- **Stage 2:** Enroll an additional 14 patients. *If 14 or more out of 26 patients respond, hCG will be considered promising for further investigation.*

If phase I trial enrolls more than 12 patients at the MTD, we will adjust the futility rule above for the two stage design with the giving number of patients enrolled at the MTD.

5 Patient Selection

Study entry is open to persons 0 to 76 years of age regardless of gender or ethnic background. While there will be every effort to seek out and include women and minority patients, the patient population is dependent upon the transplant population at the University of Minnesota.

5.1 Inclusion Criteria

- Acute graft versus host disease (GVHD) fitting one of the following categories:

High-Risk aGVHD (ARM 1)

Pediatric or adult (ages 0-76 years) HCT recipients with:

- high-risk acute GVHD, as determined either by:
 - the refined MN acute GVHD risk score [28]:
<http://z.umn.edu/MNAcuteGVHDRiskScore>
 - OR high risk on the basis of blood biomarkers (Ann Arbor Score 3 or amphiregulin ≥ 33 pg/ml) [[29, 30]]
- OR Minnesota standard (http://z.umn.edu/MNAcuteGVHDRiskScore) with aGVHD with no response to 7 days of sirolimus plus a calcineurin inhibitor.

Patients in this arm must start treatment within the first 7 days after onset of high-risk aGVHD.

or

Steroid- Dependent aGVHD (ARM 2A)

Pediatric or adult (ages 0-76 years) HCT recipient with grade II-IV steroid-dependent acute GVHD, defined as any one of the following:

- Flare of acute GVHD of at least grade II/IV severity within 8 weeks of tapering down or (off of) immunosuppression for acute GVHD, with the flare occurring on ≤ 0.5 mg/kg prednisone. This can include late-onset aGVHD and overlap syndrome.

or

Steroid-Refractory aGVHD (ARM 2B)

Pediatric or adult (ages 0-76 years) HCT recipient with grade II-IV steroid refractory acute GVHD, defined as any one of the following:

- No response of acute GVHD after at least 4 days of systemic corticosteroids of at least 2 mg/kg prednisone or equivalent
- Progression of acute GVHD within 3 days of systemic corticosteroids of at least 2 mg/kg prednisone or equivalent
- Failure to improve to at least grade II acute GVHD after 14 days of systemic corticosteroids, with initial doses of at least 2 mg/kg prednisone or equivalent
- Flare of acute GVHD of at least grade II/IV severity while on steroids at a dose >0.5 /mg/kg/day. This can include late-onset aGVHD and overlap syndrome.

- Adequate organ function at study enrollment defined as:
Renal: Serum creatinine ≤ 2.5 x ULN (within 7 days)
Cardiac: LVEF $\geq 35\%$ (within 42 days)
- Voluntary written consent (adult or parent/guardian with minor assent for 12 through 17 year olds)

5.2 Exclusion Criteria

- Progressive malignancy
- Diagnosis of a hormone responsive malignancy
- Uncontrolled infection at initiation of protocol treatment
- Current thromboembolic disease requiring full-dose anticoagulation - patients receiving pharmacologic prophylaxis for thromboembolic disease will be eligible

- Active or recent (within prior 3 months) thrombus, irrespective of anticoagulation status
- Pregnancy as assessed on baseline blood hCG level
- Unwilling or unable to stop supplemental sex hormone therapy (estrogen, progesterone, and/or testosterone preparations)
- Women or men of childbearing potential unwilling to take adequate precautions to avoid pregnancy from the start of protocol treatment through 28 days after the last treatment

6 Patient Registration

Registration will occur after the patient has signed the subject consent and eligibility is confirmed, but before any treatment has been administered. To be eligible for registration to this study, the patient must meet each criteria listed on the eligibility checklist based on the eligibility assessment documented in the patient's medical record. A copy of the eligibility checklist is under attachments within the study in OnCore.

6.1 Registration with the Masonic Cancer Center Clinical Trials Office

Upon completion of the screening evaluation, eligibility confirmation and obtaining written consent, the study coordinator or designee will enroll the patient into OnCore. At the time of registration the patient will be assigned to either Arm 1 (high-risk aGVHD) or Arm 2A (steroid-dependent aGVHD) or Arm 2B (steroid-refractory aGVHD) in OnCore.

Complete registration information is found in the study's Procedures Manual for Affiliate Sites.

Affiliate sites only: At the time of registration, the signed consents will be uploaded into OnCore as an attachment under the appropriate record.

Affiliates are responsible for fulfilling any local registration requirements.

6.2 Pregnyl® Dose Level Assignment

The dose level of Pregnyl® will be assigned based on the currently enrolling dose for the patient specific aGVHD status (Arm 1, Arm 2A or Arm 2B) and Phase.

6.3 Patients Who Are Registered and Do Not Receive Study Treatment

If a patient is registered to the study, and is later found not able to begin study treatment, for whatever reason, the patient will be removed from study and treated at the physician's discretion. The study coordinator or designee will update OnCore of the patient's non-treatment status and notify the

Principal Investigator. The reason for removal from study will be clearly documented in OnCore. Such patients will be replaced within their assigned arm (Arm 1 – high-risk aGVHD or Arm 2A (steroid-dependent aGVHD) or Arm 2B steroid-refractory aGVHD).

6.4 Patients Who Do Not Complete All Study Treatments

A patient must receive at least 3 doses of Pregnyl to be evaluable for safety/tolerability in the phase I portion of the study. If a patient receives fewer doses and discontinues study therapy for a reason unrelated to study drug toxicity, the patient will be replaced within their assigned arm, however these patients may re-consent and enroll on the study again if they are eligible at a later time.

In the phase II portion of the study, a patient must receive at least 3 doses of Pregnyl to be assessed for response in Arm 1. In Arm 2A and 2B, a patient must receive at least 6 doses to be assessed for response. If a patient does not complete the number of doses necessary for response assessment, the patient will be replaced within their assigned arm, however these patients may re-consent and enroll on the study again if they are eligible at a later time.

7 Treatment Plan

Patients may remain on their standard of care current acute GVHD therapy, including calcineurin inhibitors, sirolimus, and systemic corticosteroids at the start of study treatment, unless any of these agents are determined to unsafe due to an unforeseen complication.

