7.1 Arm 1 – High-Risk aGVHD

Standard of care immunosuppression, plus Pregnyl® (hCG supplementation) at assigned dose subcutaneously every other day for 4 doses

If a patient has a toxicity that fits the definition of dose limiting as defined in the phase I section below, the patient will discontinue study treatment.

Continue protocol treatment through day 7. Assess response at day 7:

- **If a complete or partial response**, the patient is eligible to receive Pregnyl maintenance at the same dose twice weekly for 10 doses beginning day 9 to 12. Refer to [section 9](#) for response definitions.
- **If no response**, the patient will be taken off study treatment

Pregnyl® dose level assignment will be done by treatment arm, with Arm 1 independent of Arms 2A and 2B.

For phase I, up to 5 dose levels of Pregnyl® will be tested; however dose levels -1 and -2 will be used only if dose level 1 proves too toxic.

Dose Level	Dose
-2	125 USP hCG/875 pg EGF/m ²
-1	250 USP hCG/1,750 pg EGF/m ²
1 (start)	500 USP hCG/3,500 pg EGF/m ²
2	1,000 USP hCG/7,000 pg EGF/m ²
3	2,000 USP hCG/14,000 pg EGF/m ²

The 1st 2 patients will be enrolled in dose level 1. The next cohort of 2 patients will not begin treatment until all patients in the current cohort have reached day 21 in order to assess for dose limiting toxicity (DLT).

Dose limiting toxicity (DLT) is defined as any of the following occurring by day 21 after the 1st dose of Pregnyl® (phase I component only):

- In males and females: Grade 2-4 thromboembolic event (CTCAE v4) i.e., any thrombosis more severe than a superficial venous thrombosis develops and treatment with anticoagulation is required
- In males and females: Grade 3-4 ascites (CTCAE v4)
- Specific to females: Grade 3-4 ovarian hyperstimulation syndrome, defined as the rapid development of enlarged, cystic, painful ovaries - refer to [section 11.2](#) for CTCAE grading guidance

Each new cohort of 2 patients will be assigned by the study statistician to the most appropriate dose level based on toxicity probabilities set for this study. The MTD will be identified when the total sample size of 20 patients is reached.

For the phase II the dose of Pregnyl will be that identified as the MTD during phase I.

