11.2 Adverse Event Documentation

Due to the complex medical condition of the post-transplant patient, monitoring for adverse events will focus on the following events beginning with the 1st dose of Pregnyl® and continuing for 4 weeks after the last dose. Any of these events will be documented on the study specific case report form:

- death
- anaphylaxis
- thromboembolic event
- Grade 3-4 skin injection site reaction
- Grade 3 headache
- Grade 3 gynecomastia
- Grade 3-4 ascites

In addition, the following events occurring by day 21 after the 1st dose of Pregnyl® are considered a dose limiting toxicity (DLT) and should be reported as such for patients enrolled in the Phase I component per [section 11.4](#):

- In males and females: Grade 2-4 thromboembolic event (CTCAE v4)
- In males and females: Grade 3-4 ascites (CTCAE v4)
- Specific to females: Grade 3-4 ovarian hyperstimulation syndrome, defined as the rapid development of enlarged, cystic, painful ovaries, Note: as there is no CTCAE grading for this event, the generic grading will apply as follows:

Grade	Description
1	mild; asymptomatic or mild symptoms; clinical or diagnostic observations
2	moderate; minimal or non-invasive intervention indicated

Grade	Description
3	severe or medically significant but not immediately life-threatening; hospitalization or prolongation of hospitalization indicated
4	life-threatening consequences; urgent intervention indicated

For the Phase II expansion cohort, an early study stopping rule was developed for excessive Grade 4/5 non-hematologic, non-infectious treatment probably or definitely attributed to the study drug occurring by day 28 after the last dose of Pregnyl® and is reportable per [section 11.4](#). Refer to [section 13.4](#) for details.

For both cohorts, relapse of the patient's malignancy and/or development of a new one occurring 4 weeks after the last dose is reportable per [section 11.4](#).

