The next cohort of 2 patients will not begin treatment until the last patient in the current cohort has reached day 21. Each new cohort of 2 patients will be assigned by the study statistician ([name] email: [contact]). The CRM assumes the working dose-toxicity model or power model. The probability (toxicity at d_i) = $p_i^{\exp(\alpha)}$ for each dose level i . The parameter α is distributed a priori as a normal random variable with mean 0 and variance 2. After simulation, a variance of 2 was predicted to balance both patient safety and accuracy. Pre-specified constants p_i for each dose are 1st determined by using the skeleton estimates at the beginning of the trial. After initiation of the trial and collection of events, the unknown parameter α is continuously updated. Calculation of posterior means of probability of toxicity from dose level i are calculated from Bayes theorem using the likelihood function based on a binomial distribution for the binary outcome of toxicity. After calculation of these means, each new cohort is assigned to the dose with an estimated toxicity probability closest to the pre-specified target toxicity of 25%.

Eventually the MTD will be identified when the total sample size of 20 patients is exhausted.

The dose limiting toxicity (DLT) is defined as any of the following occurring by day 21 after the 1st dose of hCG.

- In males and females: Grade 2-4 thromboembolic event (CTCAE v4)
- In males and females: Grade 3-4 ascites (CTCAE v4)
- Specific to females: Ovarian hyperstimulation syndrome, defined as the rapid development of enlarged, cystic, painful ovaries

Software within the BMA-CRMSimulator Version 2.1.0, downloaded from the MD Anderson biostatistics department website, will be used to calculate the posterior means of the toxicity probabilities for all of the doses under consideration:

<http://biostatistics.mdanderson.org/SoftwareDownload>. Dose escalation of more than one level is not permitted with this design.

Phase I component: Estimating the MTD of hCG for Arm 2B

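### Section 6.4 ties phase I evaluability to 3 doses with no follow-up requirement, which conflicts with the 21-day DLT definition and leaves very early DLTs, and losses between dose 3 and day 21, without a clear scoring rule

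*Combined protocol and SAP*

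**What the plan says.** - **Evaluability (Section 6.4, first sentence).** "A patient must receive at least 3 doses of Pregnyl to be evaluable for safety/tolerability in the phase I portion of the study". No minimum follow-up is attached.
- **Replacement (Section 6.4, second sentence).** A patient with fewer doses who "discontinues study therapy for a reason unrelated to study drug toxicity, the patient will be replaced within their assigned arm". Stops related to toxicity are outside this rule.
- **Dosing.** Arm 1 is dosed "at assigned dose subcutaneously every other day for 4 doses" (Section 7.1). Arms 2A and 2B use the same interval for 7 doses (Sections 7.2 and 7.3). Dose 3 is therefore nominally day 5 in every arm.
- **DLT window.** A listed event "occurring by day 21 after the 1st dose of hCG" (Section 13.1; same window in Sections 7.1-7.3 and 11.2). No minimum number of doses is set. Death is a targeted adverse event in Section 11.2 but is not on the DLT list.
- **Action on a DLT.** "the patient will discontinue study treatment" (Section 7.1; the same in 7.2 and 7.3).
- **Use in the model.** Section 13.1 updates the CRM with a binomial likelihood for a yes/no DLT, with no weight for partial follow-up. Section 13.2 caps phase I at 20 evaluable patients per arm, so the word evaluable sets the CRM denominator.

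**The concern.** The evaluability rule counts doses, while the endpoint is an event over 21 days. The two do not fit together in two places.

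**DLT after dose 1 or 2.** Treatment stops, so the third dose is never given and the first sentence of 6.4 is not met. The second sentence does not replace the patient, because the stop is related to toxicity. Read literally, the patient is neither in the evaluable set nor replaced.

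**Death, withdrawal or loss after dose 3 and before day 21, with no listed DLT.** The dose rule is met, the replacement rule does not apply, and the likelihood takes only 0 or 1. By default the patient enters as a complete non-DLT, although part of the window was never observed.

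If either case were scored in that way, the observed DLT rate would be too low and the CRM would lean towards higher doses. The cohorts are of 2 patients, so one misclassified patient can decide the next assignment.

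**Working it through.** **1. Reproduce the design figures.** Inputs from Section 13.1: power model p_i^exp(α), α ~ N(0, variance 2); skeleton 1, 2, 5, 10, 20% (Arms 1 and 2A) or 1, 2, 5, 10, 15, 20, 25% (Arm 2B); targets 25% and 30%; cohorts of 2 from dose level 1; 20 patients; no skipped levels on escalation; stop at posterior probability 0.90. With every DLT fully observed and 4,000 simulated trials per scenario:

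| Figure | Protocol | Recomputed |
|---|---|---|
| Table 2, top dose selected | 88% | 86.5-88.0% |
| Table 3, stopping | 11% | 11.1% |
| Table 4, top dose selected | 78% | 77-78% |
| Table 5, stopping | 11% | 8.3% |

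Table 5 stopping was not reproduced, so only the Table 3 scenario is used below.

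**2. One early DLT dropped at the next step in Section 13.2.** The starting data are the treated patients listed there, all without a DLT. Two DLTs are supposed in the next cohort of 2, one of them before dose 3. Entries are posterior mean DLT probabilities.

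| Arm, next level | Scored | Result | Assignment |
|---|---|---|---|
| 2B, level 4 (target 30%) | 2/2 | level 4: 0.288; level 5: 0.337 | stay at 4 |
| 2B, level 4 | 1/1 (one dropped) | level 4: 0.201; level 5: 0.244 | escalate to 5 |
| 2A, level 3 (target 25%) | 2/5 | level 2: 0.254; level 3: 0.368 | de-escalate to 2 |
| 2A, level 3 | 1/4 (one dropped) | level 3: 0.262 | stay at 3 |

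The assignments are the same if the skeleton is evaluated at the posterior mean of α. In Arm 1 the same exercise changes nothing: level 3 is 0.219 with 2/8 and 0.145 with 1/7, and it is the closest level to 25% both times.

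**3. Average effect if all DLTs before dose 3 were dropped.** Assume an even hazard over 21 days, so a share f = 4/21 = 19% arises before day 5. The rate among evaluable patients is p(1 − f)/(1 − pf). A true 25% appears as 21.3%, and a true 30% as 25.8%.

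**4. Loss between dose 3 and day 21.** Let q be the share lost. The documents give no day-21 figure, so q = 10-30% is an assumption. With an even DLT hazard:
- Losses spread evenly over days 5-21 leave on average 16/2 = 8 days unseen. Hidden share = q × 8/21 = 3.8%, 7.6% and 11.4% for q = 10, 20 and 30%. A true 25% reads as 24.0%, 23.1% and 22.1%.
- All losses at day 7 leave 14 days unseen. Hidden share = q × 14/21 = 6.7%, 13.3% and 20%. A true 25% reads as 23.3%, 21.7% and 20.0%.

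**5. Effect on the design.** In the Table 3 scenario, hiding 10% of DLTs lowers stopping from 11.1% to 8.1%. Selection of a dose with a true DLT rate of at least 35% rises from 31% (0.225 + 0.073 + 0.013) to 43% (0.265 + 0.127 + 0.034). A hidden share of 10% needs q = 0.10 × 21/8 = 26% with spread losses, or q = 0.10 × 21/14 = 15% at day 7.

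**The case against.** **Three doses are stated as necessary, not sufficient.** Sections 7.1-7.3 hold the next cohort until all current patients reach day 21, so the 21-day observation is part of the plan. This stands. But nothing says what to do with a patient who cannot reach day 21, and no passage offers an outcome other than 0 or 1.

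**The text points towards counting early DLTs.** The second sentence of 6.4 carves out toxicity-related stops, which has little purpose unless those patients are kept. The DLT definition runs from the 1st dose, and Section 11.2 applies it to patients enrolled in phase I, not to evaluable patients. This also stands. A reader might infer that early DLTs will be discarded and that the CRM is biased upward; the documents do not support that as fact. They support a conflict between passages.

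**A reader might also infer that all early deaths count as DLT-free.** That is too broad. Stops before dose 3 unrelated to the drug are replaced. Survivors who stop early are followed for 28 days after the last dose (Section 7.6), which is past day 21. What remains is death, withdrawal or loss between dose 3 and day 21, and even there the scoring is an inference.

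**The size rests on assumptions.** The only mortality figure is 80-100% within two years in steroid-refractory disease (Section 2). It does not give day-21 loss in any arm. Section 13.2 shows no DLT among 10 + 4 + 7 = 21 treated patients, so no case is documented in which the rule changed a dose. That does not settle how the next one would be scored.

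**Conclusion.** The concern holds as a conflict in the definition of the CRM analysis set. Section 6.4 must be reconciled with the DLT definition and with the rule that a DLT stops treatment. The early-DLT conflict matters more: one dropped DLT reverses the next assignment in Arms 2A and 2B from the Section 13.2 data, in the worked case of two DLTs in the next cohort. It does not do so in Arm 1. Counting these DLTs is the likely intent, but a second site has been added and the rule should not rest on intent.

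The gap after dose 3 is probably modest: about 4-11% of DLTs hidden with spread losses, or 7-20% with all losses at day 7. Both ranges assume 10-30% loss and an even DLT hazard that is independent of loss. An established upward bias, or a fixed figure such as 13% of DLTs hidden, would go beyond what the documents support.

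**What to change.** Rewrite the phase I part of Section 6.4, and refer to it from Section 13.1, so that the CRM analysis set contains:
- any patient with a DLT from the 1st dose through day 21, regardless of the number of doses received; and
- any patient with at least 3 doses and DLT-free follow-up through day 21.

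All other patients are replaced. This is an analysis-set definition and changes no treatment rule.

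**Cost.** Wording, plus replacements in phase I: none if nobody is lost, otherwise roughly 20/(1 − q) − 20 per arm, which is about 2 at q = 10%, 5 at 20% and 9 at 30%, with the cohort waits that follow.

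**Trade-off to state.** The set then holds DLT cases and patients followed to day 21, which shifts the observed rate slightly upward. With spread losses at q = 20% and a true 25%, the rate is 0.231/(0.231 + 0.75 × 0.80) = 27.8%. That errs towards caution and should be acknowledged in Section 13.1.
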